# Table 11:Expected Number of Cases of Virologic ZIKV Infection among Seronegative
Enrollees within 2 and 3 Years of Trial Initiation under Different Assumed
Baseline Seropositive Rates, Yearly Incidence Rates under Placebo among
Seronegatives, and Sample Sizes

Seropositive rate at baseline (%)	Total sample size (#)	Yearly incidence (under placebo)	Cases of ZIKV infections within 2 years (#)	Cases of ZIKV infections within 3 years (#)
0	7500	0.0100	78	130
	12500	0.0050	65	108
	15000	0.0050	78	130
	15000	0.0025	39	65
10	7500	0.0100	70	117
	12500	0.0050	58	97
	15000	0.0050	70	117
	15000	0.0025	35	58
	20000	0.0025	47	78
30	7500	0.0100	54	91
	12500	0.0050	45	76
	15000	0.0050	54	91
	15000	0.0250	27	45
	25000	0.0250	45	76

If the seropositive rate at baseline is no more than 30% and the yearly incidence for cases of virologic ZIKV infection is 0.005, i.e., 0.5% under placebo, then with VE of 61%, an expanded study of size 15000 reaches the targeted 90 cases of ZIKV infections within 3 years if enrollment is completed within 12 months.

# 6.4. Statistical Analysis

Study accrual is defined in this protocol as being randomized to a treatment group and receiving the first administration of study product. All accrued subjects will receive at least one product administration and therefore will provide some safety data. The safety population will include all enrolled subjects, summarized according to the actual vaccination dose received.

In **Part B**, all subjects will be tested for baseline ZIKV serostatus based on samples collected at Visit 02 prior to the first product administration. Since those with prior exposure to ZIKV may respond differently to the vaccine from those naïve subjects, safety, immunogenicity and efficacy will be analyzed within each stratum defined by baseline ZIKV status in addition to overall strata combined. **Part A** of the study is to be conducted at endemic or potentially endemic sites with baseline ZIKV serostatus tested, then safety and immunogenicity analyses will be similarly run by stratum in addition to overall strata combined.

Three types of analysis cohorts are defined. The Intent-to-treat (ITT) cohort will include all accrued subjects according to group assignment. The Per Protocol (PP) cohort will include all subjects receiving all planned vaccinations within window as assigned by the randomization schedule, and not experiencing any other major protocol deviations prior to the visit of

evaluation. The Modified intent-to-treat (mITT) analyses will include all accrued subjects who remain event-free one week after all planned product administration, where event is the primary efficacy event of a positive ZIKV PCR test result.

No multiple comparison adjustment will be employed for safety, immunogenicity, or efficacy analyses. Missing data will be primarily considered as missing completely at random in safety and immunogenicity analysis provided missing data is modest (e.g. <5-10%). For completeness, we will examine the missing data completely at random assumption and perform sensitivity analyses which weaken the missing completely at random assumption if the missing data is >10% or if the missing at random assumption is questionable. For efficacy, missing at random will be assumed and methods for handling missingness, such as multiple imputation and inverse propensity weighting, will be considered.

In general, descriptive statistics by vaccine group will be tabulated for all variables of interest, stratified by baseline ZIKV testing results. This will include point estimates (mean, geometric mean, median or proportions) and their respective 95% CI or percentile spread. Formal comparisons will use standard methods, contingency tables for categorical variables, t-tests or non-parametric analogs for comparing means or geometric means, logistic regression and analysis of covariance for model discrete and continuous variables respectively.

# 6.4.1. Baseline Demographics

Baseline characteristics including demographics and laboratory measurements will be summarized by vaccine group and stratum.

#### 6.4.2. Safety Analysis

**Reactogenicity:** The number and percentage of subjects experiencing each type of reactogenicity sign or symptom will be tabulated by severity. For a given sign or symptom, each subject's reactogenicity will be counted once under the maximum severity for all assessments.

Adverse Events: AEs will be coded into Medical Dictionary for Regulatory Activities (MedDRA) preferred terms. The number and percentage of subjects experiencing each specific AE will be tabulated by severity and relationship to treatment. For the calculations in these tables, each subject's AE will be counted once under the maximum severity or strongest recorded causal relationship to treatment.

A complete listing of AEs for each subject will provide details including severity, relationship to treatment, onset, duration and outcome.

**Safety Laboratory Values:** Safety laboratory values will be summarized using shift tables to compare baseline and follow-up values. Shift tables will be analyzed using Generalize Estimating Equations to account for the longitudinal nature of these data. The mean change from baseline along with 95% CI at each time point measured in the study will be computed. Boxplots of safety laboratory values will be generated for baseline values and for values measured during the course of the study. Each boxplot will show the 1st quartile, the median, and the 3rd quartile, with values smaller than the 1st quartile or larger than the 3rd quartiles plotted as outliers. If appropriate, horizontal lines representing boundaries for abnormal values will be plotted.

# 6.4.3. Analysis of Immune Responses

Immunogenicity will be analyzed for a variety of cohorts defined above, and specified in the SAP (Statistical Analysis Plan). At minimum these may include ITT, PP, and mITT cohorts. Assay results will be examined to determine if their distributions should be analyzed as normal, lognormal, nominal or categorical. It may also be appropriate to dichotomize the data into "responders" and "non-responders". Immunogenicity data will be analyzed at each time point where such data is collected. Longitudinal methods will be used to estimate the nature and extent of immune response decay over time. Immunogenicity will be assessed by group. To account for preexisting immunogenicity due to prior ZIKV exposure, immunogenicity will also be assessed according to baseline serostatus as a secondary analysis.

# 6.4.4. Analysis of ZIKV Incidence

Efficacy evaluation with respect to ZIKV incidence will be performed in **Part B**. Incidence rates for ZIKV cases will be described by vaccine group and by baseline ZIKV stratum for each group. Results will be treated both as dichotomous (infection, no infection) and as a time to event (infection) variables. The primary analysis will be based on the time to case of virologic ZIKV infection, i.e., when a subject is positive for ZIKV based on a PCR test. The time to ZIKV case data, accounting for censoring, will be described using Kaplan-Meier curves and efficacy computed using a Cox proportional hazards model. VE will be estimated by the hazard ratio from the Cox proportional hazards model stratified by baseline ZIKV exposure status.

The primary efficacy analysis is a test of the null hypothesis (H0): the study vaccine has VE no more than 20% in preventing ZIKV infection, i.e., VE  $\leq$  20%, where ZIKV infection is defined as virologically confirmed infection by PCR virus detection. The alternative hypothesis is that VE > 20%. The criterion for success will be that a one-sided test of H0 has p-value  $\leq$  0.025. This primary analysis will be based on the mITT cohort stratified by baseline serostatus (prior exposed to ZIKV or not). If the null VE  $\leq$  20% is not rejected, an additional test of H0\*: VE = 0 will be conducted using a one-sided type I error rate of 0.025.

The secondary efficacy analyses include the testing of this hypothesis over the two stratum combined. Another secondary analysis will test the above hypothesis H0, where ZIKV infection is defined as PCR virus detection irrespective of symptoms. The SAP will provide any necessary additional specificity and/or cohort definitions such as discussed at the beginning of Section 6.4.

# 6.4.5. Interim Analyses

# **Independent Safety Reviews:**

The PSRT will review safety data routinely throughout the study. The study will utilize both electronic database features and reviews by designated safety review personnel to identify in a timely manner if any of the safety pause rules of the study are met. The DSMB will provide an independent safety review at scheduled intervals to coincide with their biannual meeting schedule.

#### **Immunogenicity Reviews:**

**Part A:** The data in **Part A** will be used in an ongoing manner to help select the regimen to be used in **Part B**.

**Part B:** An interim analysis of immunogenicity data may be performed after the NAb assays up to and including Week 12 have been completed on a subset of subjects. Reports will be provided to the Protocol Chairs and other key investigators solely for the purpose of informing future trial-related decisions in a timely manner. The results will remain confidential and should in no way influence the conduct of the VRC 705 trial in terms of early termination or later safety or immunogenicity endpoint assessments.

#### Efficacy Reviews (Part B only):

The final efficacy analysis will occur when the total number of virologic ZIKV cases in **Part B** of the study reaches 90. Interim efficacy analysis will be performed when the total number of virologic ZIKV cases in the mITT cohort reaches 30 and 60. To preserve a one-sided type I error rate of 2.5%, the Lan-DeMets spending function will be adopted. The Lan-DeMets analog of the O'Brien-Fleming boundary, or equivalently, the nominal significance of 0.0001, 0.006, and 0.023 will be used in the two interim analyses and the final analysis, respectively, for declaring efficacy. These tests will be of the null H0: VE  $\leq 20\%$ .

To examine for harm (i.e., a greater rate of ZIKV cases in the vaccine arm) a 95% nominal CI for the hazard ratio will be calculated. A guideline for stopping is met if this CI excludes 0 in the direction of harm. Harm will be monitored after 15, 30, 45, 60, and 75 cases have accrued. Harm will be monitored using both the ITT and mITT cohorts.

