## 2.1. Purpose of the Analyses

Note, not all analyses for endpoints included in the protocol are detailed in this plan. The exploratory endpoint analyses are not included in this SAP.

In **Part A**, the primary objective is to evaluate the safety and tolerability of the vaccine. In **Part B**, the primary objectives are to evaluate the safety and efficacy of the vaccine compared to the placebo. Secondary and exploratory objectives of the study relate to immunogenicity and durability of immune responses.

The VRC 705 protocol calls for multiple planned interim analyses. During **Part A** of the study immunogenicity may be analyzed in an ongoing fashion. During **Part B** of the study the following interim analyses will be performed:

- 1. Interim immunogenicity analyses may be performed after the neutralizing antibody (NAb) assays up to and including Week 12 have been completed on a subset of subjects.
- 2. Interim efficacy analysis may be performed when the total number of ZIKV cases in the modified Intent-to-treat (mITT) cohort reaches 30 and 60.

For **Part B**, the final efficacy analysis will occur when the total number of virologic ZIKV cases in the mITT cohort reaches 90 or study completion. The final analysis of **Part A** and **Part B** will be performed and completed when all primary and secondary safety, efficacy, and immunogenicity endpoint data are available, and the study database has been locked. The study clinical database and immunogenicity/efficacy database will be locked separately; the final analysis of **Part A** and **Part B** safety data will follow the clinical database lock and the final analysis of **Part A** and **Part B** immunogenicity and efficacy data will follow the second database lock once all lab data are received and validated.

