#### **10.2.** Analysis of vaccine efficacy:

The time of ZIKV events is defined as the illness onset date recorded on the ZIKV Endpoints eCRF (for clinical cases) or date first specimen was collected with a positive PCR or other Zika result, whichever is earliest. Time to event for analysis will be as follows:

- For subjects with infection: time of ZIKV event minus date of first administration (Visit 02) + 1.
- For subjects with no infection: date of protocol completion/termination as recorded on the study status eCRF minus date of first administration (Visit 02) + 1. These subjects will be censored at their date of study completion or date of early termination.
- Subjects with or without infection may be censored from the analysis for the PP population as described in Section 6.3.

For subjects who were randomized but did not receive any product, date of randomization will be used in place of date of first administration in the definitions above.

The cumulative incidence of ZIKV cases will be presented graphically as 1 – Kaplan-Meier curves. Curves will be presented by study group and baseline ZIKV stratum and by study group combined over all subjects (Figure 27 through Figure 44, Appendix 2). Similar presentations will be displayed for virologic ZIKV cases and subclinical ZIKV cases).

Vaccine efficacy will be estimated as 1 - Hazard Ratio estimated from a Cox proportional hazard model. The primary efficacy analysis for ZIKV infection will use the following test:

H0: VE 
$$\leq 20\%$$
  
H1: VE  $\geq 20\%$ 

The criterion for success will be that a one-sided test of  $H_0$  has p-value  $\leq 0.025$ . Success will be met if the lower bound of the 95.0% confidence interval for VE estimated for the mITT population using a Cox proportional hazards model stratified by baseline ZIKV status is >20 (Table 51 through Table 53, Appendix 1).

If the null hypothesis VE  $\leq 20\%$  is not rejected, then the following will be tested using a one-sided type I error rate of 0.025.

H\*0: VE =0% H\*1: VE >0%

As secondary analyses of vaccine efficacy this hypothesis will be tested for:

- ZIKV cases without stratification for baseline ZIKV serostatus
- virologic ZIKV cases stratified by baseline ZIKV serostatus
- subclinical ZIKV cases stratified by baseline ZIKV serostatus
- subclinical ZIKV cases without stratification for baseline ZIKV serostatus

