#### Cox Proportional Hazard

SAS Code for stratified Cox Regression [4] to obtain Vaccine Efficacy and 95% CI for Vaccine Efficacy:

```
Proc phreg;
CLASS trtmnt (ref = 'placebo') / param = ref;
STRATA stratavar;
MODEL timevar*censorvar(1)=trtmnt (and any covariates)/rl;
ODS OUTPUT ParameterEstimates=ests (keep=HazardRatio HRUpperCL
HRLowerCL);
RUN;
```

Calculate the following from the estimates obtained from the PROC PHREG output:

Vaccine Efficacy = 1 – HazardRatio Lower 95% CI= 1 – HRUpperCL Upper 95% CI= 1 – HRLowerCL

Similar code will be used to fit the cox regression combined across ZIKV serostatus stratum by removing the STRATA statement on PROC PHREG.

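### The harm guideline tests a hazard-ratio interval against 0, but the no-effect value of a hazard ratio is 1

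*Combined protocol and SAP*

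**What the plan says.** Protocol 6.4.5, under the Part B efficacy reviews, defines harm as "i.e., a greater rate of ZIKV cases in the vaccine arm". To look for it, "a 95% nominal CI for the hazard ratio will be calculated". The next sentence sets the criterion: "A guideline for stopping is met if this CI excludes 0 in the direction of harm". The timing is "Harm will be monitored after 15, 30, 45, 60, and 75 cases have accrued", and "Harm will be monitored using both the ITT and mITT cohorts".

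The SAP fixes the scale. Section 10.2 says "Vaccine efficacy will be estimated as 1 - Hazard Ratio estimated from a Cox proportional hazard model", and the sample Cox code makes placebo the reference with "CLASS trtmnt (ref = 'placebo') / param = ref". The hazard ratio is therefore vaccine over placebo, and no effect means HR = 1, log HR = 0 or VE = 0.

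The SAP contains no harm rule. Its list of Part B interim analyses (section 2.1) has an immunogenicity analysis and an efficacy analysis that "may be performed when the total number of ZIKV cases in the modified Intent-to-treat (mITT) cohort reaches 30 and 60". Sections 6.2 and 6.6 add no harm look, scale or threshold.

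**The concern.** The interval in the criterion can only be the hazard-ratio interval of the sentence before it, since that paragraph mentions neither a log transformation nor a VE interval. A hazard-ratio interval from a Cox model is obtained by exponentiation, so it cannot reach 0. As written, the comparison is satisfied by data showing harm, no effect or benefit alike, and only the words about direction do any work.

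This is the only statistical threshold in either document for excess ZIKV infection on vaccine. The pause rules in Protocol 4.6 turn on related SAEs and repeated related Grade 4 events, and Protocol 5.1.1 does not record ZIKV infection as an AE unless it is serious. An excess of non-serious infections in the vaccine arm would therefore come to notice statistically only through this guideline, which is read at five looks in two cohorts.

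**Working it through.** **Inputs.** Looks at 15, 30, 45, 60 and 75 cases and a nominal 95% interval (Protocol 6.4.5); 1:1 allocation and planning effect VE 61%, i.e. HR 0.39 (Protocol 6.3.2); probability that a case is a vaccinee (1−VE)/(2−VE) = HR/(1+HR) (Protocol 6.3.2.3).

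**The plan's own figures.** The plan gives no operating characteristic for the harm guideline, so the surrounding event plan was checked first. With p0 = 4/9, p1 = 0.39/1.39 = 0.2806 and one-sided 0.025, the score formula gives

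n = [(1.960·√(p0(1−p0)) + 1.2816·√(p1(1−p1))) / (p0−p1)]² = [(0.9739 + 0.5758)/0.1639]² ≈ 89.4

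for 90% power. That agrees with Table 9 (89 cases), and power at 90 cases is 90.2%. The Lan-DeMets O'Brien-Fleming levels at 30, 60 and 90 cases come out at 0.00010, 0.0060 and 0.0231, matching those stated. The event plan is sound, and the problem is confined to the harm criterion.

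**Interval used.** For v vaccine and p placebo cases with equal person-time, HR = v/p and the interval is exp{log(v/p) ± 1.96·√(1/v + 1/p)}.

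- 8 v 7: log HR = 0.134, SE = √(1/8 + 1/7) = 0.518, interval 0.41 to 3.15. It excludes 0 and the estimate is above 1, but it shows nothing.
- 21 v 54 (75 cases, HR 0.39): log HR = −0.944, SE = √(1/21 + 1/54) = 0.257, interval 0.23 to 0.64. It shows clear benefit and still excludes 0.
- 12 v 3: log HR = 1.386, SE = √(1/12 + 1/3) = 0.645, interval 1.13 to 14.2. This lies wholly above 1.
- 11 v 4: log HR = 1.012, SE = √(1/11 + 1/4) = 0.584, lower limit 0.88. This does not.

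**Literal text with the direction phrase set aside.** The criterion is met as soon as one vaccine case exists. At VE 61% and the first look this has probability 1 − (1/1.39)^15 = 0.993.

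**Two readings over all five looks.** The number of vaccine cases follows a binomial walk with probability HR/(1+HR), stopped at the first look where the criterion is met. Reading (a): the interval excludes 0 and estimated HR > 1, i.e. v > p. Reading (b): the lower limit of the interval exceeds 1.

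| Cases | 15 | 30 | 45 | 60 | 75 |
|---|---|---|---|---|---|
| Smallest v/p meeting (a) | 8/7 | 16/14 | 23/22 | 31/29 | 38/37 |
| Smallest v/p meeting (b) | 12/3 | 21/9 | 30/15 | 38/22 | 47/28 |

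| True effect | (a) met by fifth look | (b) met by fifth look |
|---|---|---|
| VE 61% (HR 0.39) | 3.5% | 0.005% |
| VE 20% (HR 0.8) | 46% | 1.1% |
| VE 0 (HR 1) | 74% | 5.8% |
| HR 1.5 | not computed | 47% |
| HR 2 | not computed | 86% |

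**The case against.** The best defence is that no competent reader would apply the sentence literally. The same paragraph defines harm as more cases on vaccine, and excluding a null value in the direction of harm has only one workable meaning: the interval excludes equal rates on the side of more vaccine cases. Two of the three equivalent scales, log HR and VE, do have 0 as the no-effect value, so this is a shorthand slip. A DSMB statistician would probably supply the right value. On that reading the guideline behaves sensibly (5.8% at HR 1, 86% at HR 2). The 74% and 99.3% figures belong to readings that nobody intended: one lets a point estimate stand in for an interval criterion, the other disregards words that are in the sentence. The guideline is also advisory, the DSMB reviews cumulative data at least twice a year in any case, and the SAP is equally silent on the efficacy boundaries.

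Much of this stands. The intent can be inferred, no automatic stop follows, and the literal figures illustrate what the words permit; they do not predict what the DSMB would do. The objection does not make the sentence correct. The direction phrase names a side but no amount of evidence, and the stated scale and stated value do not belong together. The SAP's silence did not cause the slip, but it means that no second statement exists to resolve it.

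One limit is fairly raised. The calculation covers a single cohort, while the plan monitors ITT and mITT. If either can trigger, the rate for the full procedure is no lower than the single-cohort figure. It was not computed, and the scale error does not depend on it.

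**Conclusion.** The concern holds. The guideline names a hazard-ratio interval and compares it with a value that such an interval always excludes, so the threshold as written does not distinguish harm from chance, or even from benefit. How much this matters depends on the reading: 74% against 5.8% under no effect, and 3.5% against 0.005% at the planning VE of 61%.

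The figures assume 1:1 arms with equal person-time, a Wald interval on log HR, and one cohort. An exact or profile-likelihood interval could move a triggering split by about one case. The conclusion about the scale needs none of these assumptions.

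The 90-case target, the power and the efficacy boundaries are unaffected. Because the intent is recoverable and the guideline is advisory, the realistic harm is a dispute or inconsistency at a DSMB look. It should be fixed because this is a decision threshold that the trial relies on.

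**What to change.** Put the criterion on one scale with its matching no-effect value. In Protocol 6.4.5, replace the sentence with:

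> *The guideline for harm is met if the lower limit of the nominal 95% CI for the hazard ratio (vaccine versus placebo) exceeds 1, equivalently if the upper limit of the CI for VE is below 0.*

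Carry the same sentence, the five look times and the two cohorts into SAP 6.6, and add the harm looks to the list in SAP 2.1 so that the two documents agree. The triggering splits in the working illustrate this reading and need not be written into the plan.

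The cost is one sentence in the protocol and a short addition to the SAP. No sample size, power or alpha figure moves.

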# 6.3.2. Sample Size Considerations: Part B

**Part B** of the study targets healthy adults and adolescents ages 15 to 35 years who reside in ZIKV endemic or potential endemic regions. This age range is considered to be the range of the highest reproductive potential and therefore, this age group will likely be the initial target for a successful ZIKV vaccine. Additionally, the risk of GBS has been shown to increase with age, so

this study population excludes those who might be at higher perceived risk for GBS [54-56]. Randomization at each study site will equally allocate subjects to vaccine or placebo schedules. The randomization plan does not include provisions for replacing subjects with incomplete product administration or visit schedules.

A total of 2400 subjects will be randomized 1:1 to receive either the study vaccine or placebo. The study sample size was determined primarily based on the evaluation of vaccine efficacy (VE). The study also has ample sample size for detecting AEs, therefore meeting the primary endpoints.

To detect a VE of 61%, the trial aims to achieve 90 cases of naturally acquired virologic ZIKV infection within 2 to 3 years. If it appears this target is unlikely to be met, the study may be expanded to achieve this target. Prior to the completion of randomization, the combined vaccine and placebo incidence rate of subclinical ZIKV cases will be calculated. At each site, the blinded site-specific baseline seropositivity rate may be calculated and used to adjust the needed sample size and to aid in allocation of enrollment slots. Both types of rates will be used to help decide if the enrollment should be extended to allow for the target to be achieved. For planning purposes, we will allow for a total sample size of up to 15,000. Such a sample size could achieve our target number of virologic ZIKV cases within 3 years, assuming full accrual within 12 months, even if the placebo incidence rate is as low as 0.50% and the seropositive rate is as high as 30% among enrollees.

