# List of Abbreviations (continued)

#### 1. **PREFACE**

The Statistical Analysis Plan (SAP) for "A Phase 2/2B, Randomized Trial to Evaluate the Safety, Immunogenicity and Efficacy of a Zika virus DNA Vaccine in Healthy Adults and Adolescents" (VRC 705) describes and expands upon the statistical information presented in the protocol.

This document describes all planned analyses that will be conducted by the VRC 705 Data Center and provides reasons and justifications for these analyses. It also includes sample tables, figures, and listings (TFL) planned for the final analyses. Regarding the final analyses, this SAP follows the International Conference on Harmonisation of Technical Requirements for Registration of Pharmaceuticals for Human Use (ICH) Guidelines, as indicated in Topic E3 (Structure and Content of Clinical Study Reports), and more generally is consistent with Topic E8 (General Considerations for Clinical Trials) and Topic E9 (Statistical Principles for Clinical Trials). The structure and content of the SAP provides sufficient detail to meet the requirements identified by the Food and Drug Administration (FDA) and ICH, while all work planned and reported for this SAP will follow internationally accepted guidelines published by the American Statistical Association and the Royal Statistical Society for statistical practice.

This document contains four sections: (1) a review of the study design, (2) general statistical considerations, (3) comprehensive statistical analysis methods for efficacy and safety endpoints, and (4) a list of proposed TFLs (Appendices 1, 2, and 3).

Following any protocol amendment, this SAP will be reviewed and revised to address any changes in the protocol impacting analysis. Any deviation from the final SAP will be described and justified. The reader of this SAP is encouraged to also review the study protocol for details on conduct of the study and the operational aspects of clinical assessments.

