#### 6.6.3. Incidence Reviews (Part B only):

The study will be regularly monitored using the combined (blinded) incidence rates for ZIKV disease and for ZIKV infections. These rates will be monitored at each site and over all sites combined. Such monitoring will allow for enrollment to be expanded or curtailed at different sites.

Prior to completion of enrollment of the 2400 Part B subjects, calculations using the blinded incidence rates will be performed to estimate the expected time to achieve 90 cases of ZIKV disease. Based on these calculations, the sample size may remain fixed at 2400, be increased up to 15,000, or the trial may be stopped for lack of feasibility if this expected time is deemed excessive.

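### The SAP omits the five by-arm harm looks, and the stopping guideline, that protocol 6.4.5 requires during Part B

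*Combined protocol and SAP*

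**What the plan says.** Protocol 6.4.5, under Efficacy Reviews, sets the harm rule. The statistic is that "a 95% nominal CI for the hazard ratio will be calculated". The rule is that "A guideline for stopping is met if this CI excludes 0 in the direction of harm". The schedule is "Harm will be monitored after 15, 30, 45, 60, and 75 cases have accrued", and the populations are stated separately: "Harm will be monitored using both the ITT and mITT cohorts". None of this is conditional.

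SAP section 1 describes its own scope: "This document describes all planned analyses that will be conducted by the VRC 705 Data Center". For Part B, SAP 2.1 lists two interim analyses. One is immunogenicity; the other is efficacy, which "may be performed when the total number of ZIKV cases in the modified Intent-to-treat (mITT) cohort reaches 30 and 60". SAP 6.2 (timing) lists neither the interim efficacy analyses nor any harm look. SAP 6.6 carries over three of the four reviews in protocol 6.4.5: safety, immunogenicity and incidence. The one left out, Efficacy Reviews, holds the harm rule. The incidence review that remains is pooled: "The study will be regularly monitored using the combined (blinded) incidence rates for ZIKV disease and for ZIKV infections".

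**The concern.** The two documents disagree on a safety rule. The protocol fixes when harm is examined, in which cohorts and against what criterion. A statistician programming interim reports from the SAP would find no schedule, criterion or table shell for it. For several other topics (objectives, endpoints, sample size, randomization, blinding) the SAP simply refers to the protocol section, but it does not do so for the 6.4.5 harm rule.

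Other monitoring does not supply the missing rule. Pooled blinded incidence cannot show an imbalance between arms. ZIKV infections are not adverse events unless serious (protocol 5.1.1), so adverse-event tables will mostly not contain them. The efficacy hypotheses in SAP 10.2 are VE ≤ 20% and then VE = 0 against VE > 0, and neither is a test for harm. Protocol 8.6.1 itself says it is unknown whether vaccination changes the response to a later ZIKV infection.

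**Working it through.** **1. The plan's own figures.** Inputs from protocol 6.3.2.3 and 6.4.5: 90 cases, VE 61%, null VE 20%, one-sided 0.025, 1:1 allocation. Conditional on the total, P(case is in the vaccine arm) = (1−VE)/(2−VE), so p0 = 0.8/1.8 = 4/9 and p1 = 0.39/1.39 = 0.2806.

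Power = Φ[(|p0−p1|√n − 1.96√(p0(1−p0)))/√(p1(1−p1))] = Φ[(0.1639×9.487 − 1.96×0.4969)/0.4493] = Φ(1.292) = 90.2%. The exact binomial gives 89.0%. The stated 90% is reproduced. The Lan-DeMets O'Brien-Fleming nominal levels at 1/3, 2/3 and full information come to 0.000104, 0.00601 and 0.0231, matching the protocol's 0.0001, 0.006 and 0.023.

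**2. What the harm rule means in cases.** A confidence interval for a hazard ratio can never include 0, so the guideline is read here as excluding HR = 1 (log HR = 0). With a vaccine cases and b placebo cases, harm is flagged when the lower 95% limit of the HR exceeds 1. Two versions were used:
- Wald: log(a/b) − 1.96√(1/a + 1/b) > 0. At 15 cases, 12:3 gives 1.386 − 1.265 > 0, while 11:4 gives 1.012 − 1.144 < 0.
- Clopper-Pearson: P(X ≥ a | n, 0.5) ≤ 0.025.

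The smallest flagging vaccine-arm counts are 12/15, 21/30, 30/45, 39/60 and 47/75. Wald differs only at 60 cases, where it is 38.

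**3. Probability of a flag.** Exact binomial recursion over the looks, with P(case in vaccine arm) = HR/(1+HR). The true HRs are assumptions, because the documents give none. Mean cases counts 90 for a trial that is never flagged. Each cell gives Clopper-Pearson / Wald.

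| Assumed HR | Five looks: flagged by 75 | Mean cases | Same rule at 30 and 60 only: flagged | Mean cases |
|---|---|---|---|---|
| 1 | 5.3% / 5.8% | 87.1 / 87.0 | 3.0% / 3.9% | 88.5 / 88.2 |
| 1.5 | 45.2% / 47.4% | 69.0 / 67.8 | 31.2% / 38.5% | 75.4 / 73.2 |
| 2 | 84.5% / 85.7% | 46.8 / 45.7 | 70.3% / 77.6% | 55.9 / 53.8 |
| 3 | 99.5% / 99.6% | 27.1 / 27.0 | 97.5% / 98.6% | 36.7 / 36.3 |

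At HR 2 the Wald probabilities at successive looks are 0.2092, 0.2547, 0.1649, 0.1630 and 0.0649, which cumulate to 21%, 46%, 63%, 79% and 86%.

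**4. Comparison.** At HR 2, moving from five looks to two loses 84.5 − 70.3 = 14 points (Clopper-Pearson) or 85.7 − 77.6 = 8 points (Wald), and stopping comes about 8 to 9 cases later on average. If the optional analyses are not done, there is no scheduled by-arm look before 90 cases, against a mean of 46-47 with the protocol's looks. The two-look column is generous to the SAP, which states no harm rule at those analyses.

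**The case against.** The strongest reply is that the SAP adds to the protocol and does not replace it. SAP section 1 says it expands on the protocol's statistical content, and SAP 2.1 acknowledges that the protocol calls for several interim analyses. Nothing withdraws 6.4.5. The SAP is Version 1.0 of 11 November 2019, while Part B accrual began in July 2017 (protocol 1.4), so any look reached before the SAP existed could only have run under the protocol.

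Other routes to a by-arm view also survive. The DSMB reviews data at least twice a year and has access to the randomization code (protocol 5.6, 8.9.2; SAP 6.6.1). It may see data by group and may be unblinded (protocol 6.4.6). ZIKV infection events are a listed Part B safety parameter (protocol 6.2.1). SAP 6.2 leaves room for reviewing ZIKV episodes for safety before database lock. The SAP's Cox code outputs both confidence limits, so harm could be read off at 30 and 60 cases.

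All of that stands, and it rules out two stronger readings. A reader might infer that a harmful vaccine would not be looked for until the final analysis; the optional 30- and 60-case analyses and the DSMB reviews contradict this. A reader might also infer that vaccination-period cases, which mITT excludes, could never be compared early. But SAP 10.2 runs all efficacy analyses in ITT, mITT and PP, and in SAP 2.1 mITT only defines the case count that triggers the analysis.

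None of it restores what is missing from the SAP: the 15-, 45- and 75-case looks, a harm criterion at any look, and an obligation to perform the looks at 30 and 60.

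**Conclusion.** The conflict is real and should be reconciled. The protocol pre-specifies five by-arm harm looks with a stopping guideline; the SAP, which claims to cover all planned Data Center analyses, contains none. What is lost is the pre-specified rule, not all safety oversight.

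Under an assumed HR of 2 the cost ranges from 8-14 points of detection probability and 8-9 more cases (if the rule is applied at 30 and 60 anyway) to no scheduled by-arm look before 90 cases (if those analyses are skipped). These sizes rest on assumed hazard ratios, 1:1 case splitting conditional on the total, and HR = 1 as the intended reference. The false-flag rate of about 5-6% is for one cohort; flagging on either ITT or mITT would raise it somewhat, by an amount not computed here.

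**What to change.** In the SAP, add the harm looks to 2.1 and 6.2 and as a new item in 6.6: after 15, 30, 45, 60 and 75 cases, Cox hazard ratio with nominal 95% CI, in ITT and in mITT, reported to the DSMB. Name who runs them, and add one DSMB table shell showing cases by arm, HR and CI. Make SAP 2.1 agree with protocol 6.4.5 on whether the 30- and 60-case efficacy analyses *will* or *may* be done.

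Two things should not be carried over as they stand:
- **Scale.** Express the guideline as a CI excluding HR = 1, or log HR = 0, and correct the protocol wording at the next opportunity.
- **Trigger.** State which cases count towards 15, 30 and so on, and in which cohort. Virologic cases include subclinical ones found by retrospective PCR (protocol 4.3.1), but SAP section 10 defers analyses that need stored-sample testing until after database lock. Either the looks count only cases known in real time, or the testing must be scheduled to feed them.

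The cost is SAP text and one table shell. The protocol already requires the looks, so adding them to the SAP needs no protocol amendment. The trigger definition is the only part that could carry an operational cost, if stored samples are to be tested earlier.
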